#### **4.8. Biomarker Variables**

Biomarkers to be analyzed in this study are:

- TARC
- Total serum IgE
- Allergen specific IgEs
- Allergen specific IgG4s
- Eotaxin-3

Serum samples for measurements of biomarkers to study the pharmacodynamic activity of dupilumab in EoE patients will be collected at time points according to Section 11.2.

#### **4.9. Patient Reported Outcomes for Psychometric Validity Assessment**

The psychometric validity of 3 patient-reported outcome measures (DSQ, EoE-SQ, and EoE-IQ as described in Section 4.4.1 and Section 4.4.2) will be assessed.

## 5. STATISTICAL METHODS

For continuous variables, descriptive statistics will include the following: the number of patients reflected in the calculation (n), mean, median, Q1, Q3, standard deviation, minimum, and maximum.

For categorical or ordinal data, frequencies and percentages will be displayed for each category. Missing values at baseline will not be imputed unless otherwise specified.

All data will be summarized by the following treatment groups in each part:

1. Part B
  - Dupilumab 300mg Q2W
  - Dupilumab 300mg QW
  - Combined Dupilumab Group (For safety analysis only)
  - Placebo
2. Part C (Treatment in Part B/Treatment in Part C)
  - Dupilumab 300mg Q2W/Dupilumab 300mg Q2W
  - Dupilumab 300mg QW/Dupilumab 300mg QW
  - Combined Dupilumab Group (For safety analysis only)
  - Placebo/ Dupilumab 300mg Q2W
  - Placebo/ Dupilumab 300mg QW
  - Placebo/Dupilumab (For safety analysis only)
  - Total (For safety analysis only)

### 5.1. Demographics and Baseline Characteristics

Demographics and Baseline Characteristics will be summarized by treatment groups and for study total based on the FAS. A separate summary will be provided for Part C SAF patients who entered Part C from Part B.

### 5.2. Medical History

Medical history will be summarized by primary SOC and PT for each treatment group and for study total based on the SAF. The table will be sorted by decreasing frequency of SOC followed by PT based on the overall incidence across treatment groups.

### 5.3. Prior/Concomitant Medications/Procedures

Number and proportion of subjects taking prior/concomitant medications, prohibited medications/procedures and rescue medications/procedures will be summarized for each treatment group and study total, based on the study part specific SAFs, by ATC Level 2 and ATC Level 4, sorted by decreasing frequency of ATC Level 2 and ATC level 4 in the dupilumab treatment group.

Number and proportion of subjects taking PPIs for the treatment of EoE will be summarized by PPI therapy name.

Number and proportion of subjects undergoing prior/concomitant procedures will be summarized for each treatment group and study total, based on the study part specific SAFs, by system organ class (SOC) and preferred term (PT), and sorted by decreasing frequency of SOC and PT in the dupilumab treatment group.

In addition, the summary of prior/concomitant medications/procedures will be performed for subjects who were impacted by COVID-19 pandemic and not impacted by COVID-19 pandemic in each study period, respectively. The summary will be performed for pre-, during, and post-COVID-19 periods for subjects impacted by COVID-19, if applicable.

The detailed information of rescue medications/procedures including duration of use and incidence of use will be summarized, particularly for swallowed topical/systemic corticosteroids used to treat EoE. Kaplan Meier curves for time to first rescue use will be generated.

Separate summaries will be provided for Part B and Part C concomitant medications/procedures. For CMs/CPs taken during the follow-up period, separate summaries will be provided for patients who entered follow-up after Part C vs. patients who entered follow-up immediately after Part B. If there is a limited number of patients entering follow-up immediately after Part B, only listing will be provided.

#### **5.4. Subject Disposition**

The following summaries will be provided for each treatment group and study total (unless otherwise specified):

- The total number of screened patients (for study total only)
- The total number of randomized patients: received a randomization number from IWRS
- The total number of patients in each analysis set
- The total number of patients who discontinued the study treatment in Part B and the reasons for discontinuation (including COVID-19 related reasons)
- The total number of patients who discontinued the study during Part B, and the reasons for discontinuation (including COVID-19 related reasons)
- Number of patients who entered into Part C
- The total number of patients who discontinued the study treatment in Part C and the reasons for discontinuation (including COVID-19 related reasons)
- The total number of patients who discontinued the study during Part C, and the reasons for discontinuation (including COVID-19 related reasons)
- Number of patients who entered the 12-week follow-up period from Part B and Part C, respectively
- Number of patients who had occurrence(s) of visits impacted by the COVID-19 pandemic and reasons

Summary table of protocol deviations in each study treatment period will be provided.

## **5.5. Extent of Study Treatment Exposure and Compliance**

### **5.5.1. Measurement of Compliance**

Compliance with protocol-defined study drug administration will be calculated separately for Part B and Part C as follows:

$$\text{Treatment Compliance} = (\text{Number of study drug injections during the respective study part}) / (\text{Number of planned study drug injections during the respective study part}) \times 100\%$$

The extended dosing will be also be counted as QW for calculation of treatment compliance.

Treatment compliance will be summarized separately for Part B and Part C as a continuous variable with descriptive statistics for each treatment group. Treatment compliance will also be presented by the following specific ranges for each treatment group: <80% and ≥80%.

### **5.5.2. Exposure to Study Drug and Observation Period**

The duration of exposure to study drug is calculated separately for Part B, Part C, and the overall study as follows:

$$(\text{Date of last study drug injection in the respective study part} - \text{date of first study drug injection in the respective study part}) + 7$$

Note: exposure will be calculated based on the last study drug injection date and first study drug injection date regardless of temporary dosing interruption or dosing extension due to COVID-19. For patients with extended dosing due to COVID-19, the duration of exposure may exceed 24 weeks for Part B or 28 weeks for Part C as study design.

Summary of exposure to study drug will include the number of study drug doses administered and the duration of exposure. Duration of exposure will be summarized for each treatment group using number of patients, mean, SD, minimum, median, Q1, Q3, and maximum. These summaries will be provided for Part B and Part C separately.

In addition, the duration of exposure will be summarized categorically by counts and percentages for each of the following categories and cumulatively by these categories as well:

≥ 7 days, ≥ 14 days, ≥ 21 days, ≥ 28 days, ≥ 35 days, ≥ 42 days, ≥ 49 days, ≥ 56 days, ≥ 63 days, ≥ 70 days, ≥ 77 days, ≥ 84 days, ≥ 91 days, ≥ 98 days, ≥ 105 days, ≥ 112 days, ≥ 119 days, ≥ 126 days, ≥ 133 days, ≥ 140 days, ≥ 147 days, ≥ 154 days, ≥ 161 days, ≥ 168 days, with an increment of 1 week for each subsequent category.

In addition, for patients who received at least 1 dose of dupilumab, the total duration of exposure to dupilumab during the study (throughout Part B and Part C) is calculated as:

$$(\text{Date of last study drug injection in the study} - \text{date of first dupilumab injection}) + 7$$

The duration of observation period during the study is calculated as:

$$[\text{Date of the last study visit} - \text{date of the first study injection}] + 1.$$

The duration of observation period will be summarized descriptively using number of patients, mean, SD, median, Q1, Q3, minimum and maximum. In addition, the number (%) of subjects with observation periods will be presented by specific time periods. The time periods of interest is specified as:  $\geq 8$  days,  $\geq 15$  days,  $\geq 22$  days,  $\geq 29$  days,  $\geq 36$  days,  $\geq 43$  days,  $\geq 50$  days,  $\geq 57$  days,  $\geq 64$  days,  $\geq 71$  days,  $\geq 78$  days,  $\geq 85$  days,  $\geq 92$  days,  $\geq 99$  days,  $\geq 106$  days,  $\geq 113$  days,  $\geq 120$  days,  $\geq 127$  days,  $\geq 134$  days,  $\geq 141$  days,  $\geq 148$  days,  $\geq 155$  days,  $\geq 162$  days,  $\geq 169$  days,  $\geq 183$  days, with an increment of 1 week for each subsequent category.

## 5.6. Analyses of Efficacy Variables

The analyses of efficacy variables are described in the subsections below and summarized in Section 11.1. The intercurrent events, strategies, and the corresponding missing data handling approaches for the primary estimands of interest for the co-primary endpoints and selected secondary endpoint are provided in Appendix 11.1.1.

### 5.6.1. Analysis of Co-Primary Efficacy Variable(s)

#### Histologic response (binary endpoint)

The proportion of patients achieving a histologic response of peak esophageal intraepithelial eosinophil (eos) count (from all 3 regions) of  $\leq 6$  eos/hpf at week 24 will be analyzed using the Cochran-Mantel-Haenszel (CMH) test to assess the difference in the proportion of responders in the FAS adjusting for the randomization stratification factors (age group [ $\geq 18$  vs.  $\geq 12$  to  $< 18$  years of age] and use of PPI at randomization [yes vs. no]). Estimates of treatment difference and its 95% confidence interval will be presented.

Data may be collected after the patient discontinued treatment and will be included in the analyses.

To account for use of rescue treatment (see Section 0), patients will be considered as non-responder for all time points subsequent to the use of rescue treatment in the primary analysis.

If week 24 biopsy is performed after the date when the first dose of Part C study drug is administered, patients will be considered as non-responder in the analysis.

Due to COVID-19 restrictions, patients may postpone the week 24 visit until an in-clinic visit can be done for biopsy. Before the biopsy procedure could be performed, study drug would be shipped to patients directly to enable them to extend their current assigned dose regimen of study drug. The data from those delayed week 24 visits will be used in the primary analysis as long as the patients keep the extended dosing before biopsy. However, for patients in whom extended dosing due to COVID-19 is interrupted (i.e. 2 or more consecutive doses or 5 or more doses in total missing during extended dosing period), their week 24 biopsy data will be set to missing and then imputed using MI.

Missing data at week 24 will be handled according to the reason for missingness as follows:

- If the peak esophageal intraepithelial eosinophil count at week 24 is missing due to COVID-19 pandemic, the data will be imputed by multiple imputation (MI) using a random seed number of 6681774 for 10 times based on patients who have non-missing eosinophil counts at week 24. The MI will utilize the regression method with treatment group, randomization stratification, baseline eosinophil count, and week 24 eosinophil count included in the regression model. The imputed week 24 eosinophil counts will

determine whether that patient will be classified as a responder or non-responder. The results from each imputed dataset will be combined according to Rubin's formula (Rubin, 1987).

- If a patient has missing value for the histological response (peak esophageal intraepithelial eosinophil count) at week 24 due to reasons not related to the COVID-19 pandemic, the patient will be classified as a non-responder at week 24.

The complete dataset after the above steps will be analyzed by the CMH test.

#### DSQ total score (continuous endpoint)

The absolute change from baseline in the DSQ total score at week 24 will be analyzed using an analysis of covariance (ANCOVA) model for the FAS with treatment group, randomization stratification factors, and relevant baseline measurement as covariates included in the model. The cumulative distribution function (CDF) of the absolute change from baseline in the DSQ total score at week 24 will be graphed to present the between-treatment-group differences at each level of the change.

Data may be collected after the patient discontinued treatment and will be included in the analyses.

To account for use of rescue treatment (see Section 0), data will be set to missing for all time points subsequent to the use of rescue treatment in the primary analysis.

For patient with missing value or data set to missing after rescue for the DSQ total score at week 24, their data for Week 24 will be imputed by MI based on patients who remained in the trial with observed values relevant to analysis. To account for the uncertainty in the imputation, missing data at week 24 will be imputed 50 times to generate 50 complete datasets by using the MI procedure in Statistical Analysis Software (SAS).

MI will follow the 2 steps below using a random seed number of 6681774 in both steps:

1. Step 1: Use the Markov Chain Monte Carlo (MCMC) method to fill in intermittent missing values (ie, those missing values followed by observed values at subsequent visits) so that a monotone missing pattern will be formed.
2. Step 2: Using the datasets from step 1, missing data through week 24 will be imputed using the regression method with treatment group, randomization stratification, relevant baseline measurement, and post-baseline measurement up to week 24 included in the regression model.

#### SAS syntax code for MI:

```
proc mi data=mi1 out=mi2 noprint nimpute=50 seed=6681774;  
  mcmc impute=monotone;  
  var val _;  
run;  
proc mi data=mi3 out=mi4 nimpute=1 seed=6681774;  
  class trtpn ASTRAT1 ASTRAT2 ;  
  monotone reg;  
  var trtpn ASTRAT1 ASTRAT2 val _;  
  by _imputation_ ;  
run;
```

[figure not shown]
Once imputations are made, the week 24 data of each of the complete datasets will be analyzed using ANCOVA. The results from the 50 analyses on the complete datasets will be combined to generate a valid overall statistical inference according to Rubin's formula (Rubin, 1987) using the SAS MIANALYZE procedure.

During the COVID-19 pandemic, DSQ data continued to be collected by the electronic handheld devices that were with the patients at home. This is consistent with how the DSQ data was collected for the entirety of the study and does not require consideration for COVID-19 impact in the analysis.

***Handling of DSQ Data Collected During the Electronic Handheld Device Malfunction Period***

In the normal flow of DSQ diary question on the electronic handheld device, patients are directed to question 2 if they answer Yes to question 1 and will be directed to question 1a only if they answer No to question 1 (Figure 3).

**Figure 3: Flow Diagram of DSQ eDiary**

[figure not shown]
When the YPrime Change Control Form (CCF) 023 update was released on 13Mar2020, it caused a DSQ navigation error issue to some devices (listed in Section Section 11.7) **after patients synchronized their devices** with the YPrime eCOA system (this marks the start of the period when patient's device did not direct DSQ questions properly). Details are reported in a note to file for this issue (documented on 15Jan2021 by eCOA vendor).

A software update to resolve this malfunction was sent to devices on 27Mar2020 and impacted patients were instructed to upgrade the device software to fix the issue. The date when each affected patient upgraded the software on their device is provided in Section 11.7.

As a result, the devices of 6 patients randomized in Part B were affected by this navigation malfunction and irregular response patterns (as shown in Figure 4) were observed from all these 6 patients using the affected devices.

**Figure 4: Response Patterns of DSQ eDiary**

In the primary analysis, for patients using the affected devices, the daily DSQ scores will be set to missing for all days during the time when patient’s device did not direct DSQ questions properly. Diary entries are considered as “not completed” on the affected days and thus will not contribute to the requirement of a minimum of 8 diary entries during a 14-day period to calculate the DSQ total score for that period.

Sensitivity analyses

Sensitivity analyses will assess alternative methods to impute missing data and include the following for the co-primary endpoints.

**Histologic responder:**

1. Tipping point analysis: To assess the robustness of analysis results under MNAR (missing not at random) assumption, a delta-adjusting pattern-mixture approach for tipping point analysis (Ratitch, 2013) will be conducted for the co-primary endpoints. The impact from missing data on the comparisons in proportion of patients achieving peak esophageal intraepithelial eosinophil count (from all 3 regions) of  $\leq 6$  eos/hpf at week 24 between each Dupilumab group and placebo control group will be examined, by adjusting for stratification factors:
  - A sequence of analyses will be performed with the adjustment to artificially decrease the response rate in active treatment group and increase the response rate in placebo group with a fixed and definite set of values for data imputation.
  - For each combination of increasing response rate in placebo and decreasing response rate in , multiple imputed datasets will be generated and analyzed using CMH test. The results obtained from multiple imputed datasets will be combined to generate statistical inference, i.e. p-value and treatment difference between active treatment group and placebo group.

- A “tipping point” will be identified while the result is no longer statistically significant (i.e. p-value >0.05).
2. Sensitivity analyses for different methods of data handling from delayed week 24 biopsy:
    - a. All the observed data from week 24 biopsy will be used regardless of dosing interruption or out of week 24 window per protocol. Then the same rule on the missing data handling in primary analysis will be applied.
    - b. Data will be set to missing for patients with week 24 biopsy performed 3 weeks or more later than target date due to COVID-19, i.e. study day of week 24 biopsy > 190. The missing for those patients will be considered as missing due to COVID-19. Then the same rule on the missing data handling in primary analysis will be applied.
    - c. Data will be set to missing for patients with week 24 biopsy performed out of window per protocol. The missing for those patients will be considered as missing due to COVID-19. Then the same rule on the missing data handling in primary analysis will be applied.

An exploratory analysis will also be performed for patients with week 24 biopsy performed out of window per protocol due to COVID-19, i.e. study of week 24 biopsy > 176.

**DSQ total score:**

1. Tipping point analysis: To assess the robustness of analysis results under MNAR (missing not at random) assumption, a delta-adjusting pattern-mixture approach for tipping point analysis ([Ratitch, 2013](#)) will be conducted for the co-primary endpoints. The impact from missing data on comparisons in absolute change in DSQ score from baseline to week 24 between each Dupilumab group and placebo control group will be examined, by adjusting for stratification factors:
  - A sequence of analyses will be performed by adding a sequence of positive values in placebo group and subtracting a sequence of positive values in active treatment group for data imputation.
  - For each combination of adding and subtracting values, multiple imputed datasets will be generated and analyzed with the ANCOVA model. The results obtained from multiple imputed datasets will be combined using Rubin’s formula to generate statistical inference, i.e. p-value and LSmean of treatment difference between active treatment group and placebo group.
  - A “tipping point” will be identified while the result is no longer statistically significant (i.e. p-value >0.05).
2. A minimum of 4 diary entries (including days when patient responded ‘No’ to question 1) per week is required to derive a standardized total score for each 14-day period. The analysis method will be as same as the primary analysis.
3. DSQ will be scored using an alternative algorithm (detailed in section 4.4.1), i.e. assigning a DSQ daily score of 6 if patients do not eat solid food due to EoE. The analysis method will be as same as the primary analysis.

As in the primary analysis, DSQ data collected during the time when patient’s device did not direct DSQ questions properly will not be used in the above sensitivity analyses.

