### 2.3. Sample Size and Power Considerations

Efficacy assessment employs the following co-primary endpoints measuring histologic and clinical symptoms of disease, respectively:

- Proportion of patients achieving peak esophageal intraepithelial eosinophil count of  $\leq 6$  eos/hpf at week 24
- Absolute change in Dysphagia Symptom Questionnaire (DSQ) score from baseline to week 24

The assumptions used in sample size calculations are based on results from Part A of the study as below:

- The proportion of patients achieving peak esophageal intraepithelial eosinophil count of  $\leq 6$  eos/hpf at 24 weeks was 5.1% in placebo group and 59.5% in dupilumab 300mg QW group with a treatment difference of 55.4%
- The mean (standard deviation [SD]) of change from baseline in DSQ total score at week 24 was -9.6 (15.2) in placebo and -21.9 (14.6) in the dupilumab 300mg QW group with a treatment group difference of -12.3.

Based on the Part A study results, the planned sample size for Part B is approximately 70 patients in each treatment group such that for the comparison of each dupilumab treatment group to placebo:

- This sample size will yield >99.9% power to detect a treatment difference of 55.4% in the proportion of patients achieving peak esophageal intraepithelial eosinophil count of  $\leq 6$  eos/hpf at week 24 between placebo (5.1%) and each dupilumab treatment group (59.5%) at a 2-sided significant level of 5% using Fisher's exact test.
- This sample size will provide >99.9% power to detect a treatment difference of -12.3 points in the mean change from baseline in the total DSQ score to week 24 at a 2-sided significance level of 5% using a two-sample t-test, assuming a common SD of 15.0.

Therefore, the sample size of 70 patients/arm will provide an overall power of >99.9% (99.9%  $\times$  99.9%) for the co-primary endpoints, assuming no negative correlation between the two endpoints. In Part B, the same treatment effect for the two 300 mg dupilumab dose regimens (ie, QW and Q2W) is assumed.

A dropout rate of 15% is assumed for the sample size calculations.

[figure not shown]
Sample size calculations were made using nQuery Advisor 7.0.

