### **4.4. Efficacy Variable**

#### **4.4.1. Primary Efficacy Variable (s)**

The co-primary endpoints for Part B are:

- Proportion of patients achieving peak esophageal intraepithelial eosinophil count (from all 3 regions) of  $\leq 6$  eos/hpf at week 24
- Absolute change in DSQ score from baseline to week 24

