### **Dysphagia Symptom Questionnaire (DSQ) (Adapted from Hudgens, 2017)**

Question Number	Response Option	Score
1. Since you woke up this morning, did you eat solid food?	No	No score assigned
	Yes	No score assigned
[REDACTED]	[REDACTED]	[REDACTED]
	[REDACTED]	[REDACTED]
	[REDACTED]	[REDACTED]
	[REDACTED]	[REDACTED]
2. Since you woke up this morning, has food gone down slowly or been stuck in your throat?	No	0
	Yes	2
3. For the most difficult time you had swallowing food today (during the past 24 hours), did you have to do anything to make the food go down or to get relief?	No, it got better or cleared up on its own	0
	Yes, I had to drink liquid to get relief	1
	Yes, I had to cough and/or gag to get relief	2
	Yes, I had to vomit to get relief	3
	Yes, I had to seek medical attention to get relief	4
4. The following question concerns the amount of pain you have experienced when swallowing food. What was the worse pain you had while swallowing food over the past 24 hours? b	None, I had no pain	0
	Mild	1
	Moderate	2
	Severe	3
	Very Severe	4

a DSQ is modified with the addition of Question 1a when response to Question 1 is ‘No’.

b Question 4 does not assess dysphagia and is considered a standalone item to be evaluated as an exploratory outcome.

The DSQ score is calculated based on the daily responses to question 2 (frequency) and question 3 (severity) over a 14-day period using the formula from (Hudgens, 2017):

$$DSQ\ Score = \frac{(sum\ of\ points\ from\ questions\ 2\ and\ 3\ from\ daily\ DSQ\ diary) \times 14\ days}{number\ of\ diary\ days\ reported\ with\ non-missing\ data}$$

To calculate the DSQ score, a minimum of 8 diary entries (including days when patient responded ‘No’ to question 1) is required for each 14-day period to derive a standardized total score based on the cumulative scores through 14 days. If there are less than 8 diary entries for a 14-day period, the DSQ score is considered to be missing for that period. The primary analysis will be based on DSQ score calculated using this algorithm. If there are multiple diary entries on the same day, the first entry on that day will be used in calculating DSQ score for analysis. DSQ scores can theoretically range from 0 to 84, with a lower score indicating less-frequent or less-severe dysphagia.

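### The DSQ tipping-point analysis shifts imputed values in dupilumab's favour, so it cannot find a tipping point or test robustness to unfavourable missing data

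*SAP*

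**What the plan says.** SAP Section 5.6.1 (Sensitivity analyses, DSQ total score, item 1) gives the purpose as "To assess the robustness of analysis results under MNAR (missing not at random) assumption". The method is a delta-adjusted pattern-mixture analysis, carried out by "adding a sequence of positive values in placebo group and subtracting a sequence of positive values in active treatment group". Each pair of shifts is analysed by ANCOVA on multiply imputed data and combined by Rubin's formula. The tipping point is where p rises above 0.05.

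The direction of the scale is set in SAP Section 4.4.1: "DSQ scores can theoretically range from 0 to 84, with a lower score indicating less-frequent or less-severe dysphagia". The endpoint is "Absolute change in DSQ score from baseline to week 24", and SAP Section 2.3 reports the Part A mean changes as negative in both arms: -9.6 on placebo and -21.9 on dupilumab QW.

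The matching histology analysis, just before it in Section 5.6.1, is designed to "artificially decrease the response rate in active treatment group and increase the response rate in placebo group".

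**The concern.** A tipping-point analysis makes the imputed data progressively less favourable to the active arm and asks how far one must go before the result is lost. On a scale "with a lower score indicating less-frequent or less-severe dysphagia", adding to placebo makes placebo worse and subtracting from dupilumab makes dupilumab better. The procedure therefore walks away from the p > 0.05 boundary that it is meant to find. The histology version penalises dupilumab and helps placebo, so the two rules in one section point in opposite directions.

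The stake is a co-primary endpoint on which success depends. The primary DSQ analysis imputes missing values, and values set to missing after rescue, from patients with observed data. That is a missing-at-random type of assumption. In Section 5.6.1 the tipping-point analysis is the only graded challenge to it. Run as written, it would report no tipping point for any comparison that starts significant, however patients with missing data actually fared.

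**Working it through.** **Inputs from the SAP.** Section 2.3: n = 70 per arm; Part A mean changes (SD) of -9.6 (15.2) on placebo and -21.9 (14.6) on dupilumab QW; common SD 15.0; two-sided 5% level; 15% dropout; equal effect assumed for QW and Q2W. Section 4.4.1: scale 0 to 84, lower is better.

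**Assumption not in the documents.** The fraction m of week-24 DSQ values that is imputed, taken as equal in the two arms. The dropout figure of 15% is used as the central value, with 5% and 30% alongside.

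**Plan's own figures.** Difference: -21.9 - (-9.6) = -12.3, as stated. Power: 12.3 / (15 × √(2/70)) = 4.85, and Φ(4.85 - 1.96) = 99.8%. With 59.5 per arm after 15% dropout it is 99.4%. The SAP states above 99.9%, so the set-up is reproduced closely, though neither figure strictly exceeds 99.9%.

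**Effect of the shifts.** Only imputed values are shifted, so each arm mean moves by m times its shift:

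- difference = -12.3 + m(δ_dupilumab - δ_placebo)
- SE² = 2·SD² / [n(1 - m)] + m(1 - m)(δ_placebo² + δ_dupilumab²) / n

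As written (placebo +δ, dupilumab -δ), the difference is -12.3 - 2mδ. With the signs reversed it is -12.3 + 2mδ.

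Example, m = 0.15 and δ = 20: SE² = 450/59.5 + 0.1275 × 800/70 = 7.56 + 1.46 = 9.02, so SE = 3.00. As written, z = -18.3/3.00 = -6.09. Reversed, z = -6.3/3.00 = -2.10.

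Results at 15% missing:

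| δ | As written: difference (p) | Signs reversed: difference (p) |
|---|---|---|
| 0 | -12.3 (7.7e-6) | -12.3 (7.7e-6) |
| 10 | -15.3 (5.5e-8) | -9.3 (0.00096) |
| 20 | -18.3 (1.1e-9) | -6.3 (0.036) |
| 30 | -21.3 (9.9e-11) | -3.3 (0.32) |
| 40 | -24.3 (3.1e-11) | -0.3 (0.93) |

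At δ = 84, the full width of the scale, the written rule gives -37.5 (p = 7.9e-11).

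First shift at which p exceeds 0.05, searching up to 200:

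| Missing | As written | Signs reversed | Dupilumab worsened only |
|---|---|---|---|
| 5% | none | 57.4 | 101.0 (beyond the scale) |
| 15% | none | 21.2 | 39.8 |
| 30% | none | 10.3 | 20.0 |

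**Weaker effects.** Starting from differences of -5.5 to -9.0 that are significant at δ = 0, with 1% to 30% missing, the written rule also produces no tip within 84 points.

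**Simulation.** Forty trials were simulated with 50 regression imputations, ANCOVA and Rubin's rules, at 15% missing and an assumed baseline DSQ of mean 35, SD 12. As written, the median p fell from 1.8e-5 at δ = 0 to 4.3e-9 at δ = 20, and no trial exceeded 0.05 at any shift tested. With the signs reversed at δ = 20, the median p was 0.053 and 55% of trials exceeded 0.05.

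**The case against.** The best defence of the wording is that the shift applies to the size of the improvement, so that adding to placebo means more improvement. Section 5.6.1 does not say exactly which quantity is shifted. However, it names the absolute change in DSQ as the quantity examined, and nowhere do the documents define improvement as positive. A programmer following the text would implement the wrong direction.

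Four narrower points have some force.

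- **Other checks exist.** Data after treatment discontinuation are kept, two supplemental analyses vary the handling of rescue, and SAP Appendix 11.1.2 lists LOCF and WOCF for this endpoint. Protocol Section 10.4.3.1 also names MMRM and LOCF as options. But the supplemental analyses still impute missing values by the primary method, and LOCF and WOCF are single imputations without a graded shift. This remains the only delta-adjusted test of missing DSQ values.
- **The impossibility of tipping is not absolute.** With an unbounded shift, z tends to √(2nm/(1 - m)), which is 1.69 at 2% missing, so variance inflation alone could eventually cross the boundary. At 15% missing z peaks near δ = 50 (6.69) and then declines, so p does not fall at every step. No tip occurs within the 84-point scale. A comparison that is non-significant from the start has nothing to tip.
- **The missing fraction is illustrative.** Retaining off-treatment data lowers it and removing post-rescue data raises it. That is why a range is shown.
- **This is a sensitivity analysis.** The primary estimate, its p-value and the testing hierarchy do not change, and the intended direction can be inferred from the histology rule. That makes a sign slip the likely cause, but the written rule still cannot do its job.

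**Conclusion.** The concern holds. Against the SAP's own scale and its own histology rule, the DSQ shifts have the wrong sign. Under the planning assumptions (70 per arm, difference -12.3, SD 15.0, equal missingness in the two arms), the written rule never reaches p > 0.05 at 5%, 15% or 30% missing. The correct direction tips at about 57, 21 and 10 points respectively, all within the scale. These thresholds depend on the assumed missing fraction; the direction of the error does not. The shifts are formally missing-not-at-random scenarios, but only ones that favour dupilumab. A finding of no tipping point would therefore carry no evidence of robustness. This must be corrected before the analysis is run.

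**What to change.** Reword item 1 of the DSQ sensitivity analyses in SAP Section 5.6.1. Positive shifts, defined as worsening, are added to imputed values in each dupilumab arm, and positive shifts, as improvement, are subtracted from imputed values in placebo. Report the pairs of shifts at which p first exceeds 0.05, separately for QW and Q2W.

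In the same edit, state the grid of shifts, include a zero placebo shift so that worsening dupilumab alone is covered, and say how shifted scores outside 0 to 84 are handled.

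The sign correction costs one sentence of SAP text and one sign in the program. No new data are needed, and the primary analysis and the testing hierarchy stay as they are.
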